8.5 Premature Termination of the Trial

The investigator or the sponsor may terminate this trial prematurely for any reasonable cause. The Independent Ethics Committees (IECs) and Competent Authorities (CAs) should be informed promptly.

Conditions that may warrant termination include, but are not limited to:

- The discovery of an unexpected, significant, or unacceptable risk to the subjects enrolled in the trial, or potential trial subjects

A decision on the part of the sponsor to suspend or discontinue development of the IMP

If the CA obtains information that raises doubts about the safety or scientific validity of the clinical trial, the CA can suspend or prohibit the trial. Before the CA reaches its decision, it shall, except where there is imminent risk, ask the sponsor and/or the investigator for their opinion, to be delivered within one week (Directive 2001/20/EC, Article 12, Section 1).

If the trial is prematurely terminated or suspended for any reason, the investigator/institution should promptly inform the trial subjects and should assure appropriate therapy and Follow-up for the subjects.

9 TREATMENT OF SUBJECTS

9.1 Investigational Medicinal Products

9.1.1 Treatment Regimens

Subjects will be randomised to receive double-blind treatment for up to 24 weeks with either:

- inhaled molgramostim (300 µg) administered once daily,
- inhaled molgramostim (300 µg) and matching placebo administered intermittently (12 cycles of seven days molgramostim followed by seven days placebo; both administered once daily) or
- inhaled placebo administered once daily.

In the Follow-up period all subjects will receive treatment with inhaled molgramostim (300 µg) administered intermittently (12 or 24 cycles of seven days molgramostim followed by seven days off-treatment) for 24 or 48 weeks. For subjects who entered the Follow-up period before Amendment 11 was approved by the national authorities, treatment with molgramostim in the Follow-up period is not mandatory.

Treatment with molgramostim in the Follow-up period should be discontinued in case of disease worsening and/or safety concerns.

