After completion of the double-blind treatment period, subjects will be assigned to an open-label treatment Follow-up period of 24-weeks or 48-weeks to collect long term outcomes following rhGM-CSF treatment. All subjects who complete the 24-week Double-blind treatment period (regardless of whether they completed trial treatment or discontinued trial treatment prematurely) will enter the open-label period so that as much information as possible can be collected regarding the use of molgramostim in this rare disease. During the open-label Follow-up period subjects will be treated with molgramostim 300 µg daily in an intermittent regimen of 7 days on- and 7 days off-treatment. The data from the open-label Follow-up period will be analysed descriptively and reported separately.

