During the trial, WLL will be applied as rescue therapy. The criterion for performing WLL is clinical worsening of aPAP based on symptoms, reduced exercise capacity and/or findings of hypoxemia or desaturation according to the Investigator's judgement. The reason(s) for conducting WLL will be documented. Subjects undergoing WLL during the Double-blind treatment period will continue double-blind trial treatment. All subjects completing the 24-week Double-blind treatment period will enter a 24- or 48-weeks Follow-up period and will receive open-label treatment with inhaled molgramostim 300 μg daily for 7 days, followed by 7 days off-treatment. This cycle will be repeated for 12 or 24 weeks depending on when the subject is enrolled in the trial. Open-label treatment in the last 24 weeks of the Follow-up period is not mandatory for subjects who have entered this period before amendment 11 was approved by the national authorities.

After completion of both the Double-blind treatment and Follow-up trial periods, subjects who require further treatment will be offered treatment with molgramostim in a Compassionate Use Programme, where national regulations so allow.

Figure 1 Overall Trial Design

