8.3 Exclusion Criteria

Patients meeting any of the following criteria will not be permitted to enter the trial:

- Diagnosis of hereditary or secondary PAP
- WLL within one month of Baseline
- Treatment with GM-CSF within three months of Baseline
- Treatment with rituximab within six months of Baseline
- Treatment with plasmapheresis within three months of Baseline

- Treatment with any investigational medicinal product within four weeks of Screening
- Concomitant use of sputum modifying drugs such as carbocystein or ambroxol
- History of allergic reactions to GM-CSF
- Connective tissue disease, inflammatory bowel disease or other autoimmune disorder requiring treatment associated with significant immunosuppression, e.g. more than 10 mg/day systemic prednisolone
- Previous experience of severe and unexplained side-effects during aerosol delivery of any kind of medicinal product
- History of, or present, myeloproliferative disease or leukaemia
- Known active infection (viral, bacterial, fungal or mycobacterial)
- Apparent pre-existing concurrent pulmonary fibrosis
- Any other serious medical condition which in the opinion of the investigator would make the patient unsuitable for the trial

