8.4.2 Discontinuation of Double-Blind Treatment

Subjects may be discontinued from double-blind treatment and assessments at any time, if deemed necessary by the investigator.

Potential reasons for discontinuation of double-blind treatment are:

- Lack of efficacy/worsening of disease
- Unacceptable AE

- Serious hypersensitivity reaction
- Pregnancy

Those who discontinue double-blind treatment will not automatically be withdrawn from the trial but will be encouraged to continue to follow the same visit schedule.

For example: if double-blind treatment is discontinued at Week 8 (Visit 4) the subject will be encouraged to attend the remaining visits in the Double-blind treatment period (Weeks 12, 16, 20 and 24) and continue into the Follow-up period. If the subject is reluctant to agree to 4-weekly visits, the investigator should request attendance at Week 24 (Visit 8) as a minimum.

The reason and date the subject is discontinued from double-blind treatment will be documented in the eCRF.

Subjects who fulfil the criteria for rescue treatment will be scheduled for a WLL as described in *Section 9.4*. Subjects receiving a WLL should continue Double-blind treatment and attend the remaining visits in the Double-blind treatment period and then continue into the Follow-up period.

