11.8 Pregnancy

Female subjects will be instructed to notify the investigator immediately if they become pregnant during the trial. Male subjects will be instructed to notify the investigator immediately if their female partner becomes pregnant. Pregnant subjects will be withdrawn from further trial treatment. The subjects will also be instructed to report pregnancies discovered after the last visit, if they believe that conception occurred during their participation in the trial.

A pregnancy as such is not an AE, unless there is a possibility that the IMP has interfered with the efficiency of any contraceptive measures. However, the investigator should report pregnancies according to the procedures and timelines described for reporting of SAEs, *Section 11.4*. The pregnancy report form should be used instead of the SAE form.

The pregnant subject or partner will be followed until the end of the pregnancy. Any complication during the pregnancy should preferably be reported as an AE. The outcome of the pregnancy must be reported on the pregnancy report form. Any spontaneous abortion, stillbirth, birth defect/congenital anomaly, death, or other serious infant condition must be reported and followed up as an SAE.

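### The protocol gives open-label molgramostim to every subject who reaches Week 24, whatever the reason for an earlier stop; this contradicts the pregnancy rule and is not reconciled with the other discontinuation reasons

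*Protocol*

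**What the plan says.** **Who gets open-label drug.**
- Protocol 9.1.1: "In the Follow-up period all subjects will receive treatment with inhaled molgramostim".
- Protocol 7.1: "All subjects completing the 24-week Double-blind treatment period will enter a 24- or 48-weeks Follow-up period and will receive open-label treatment".
- Protocol 5.2 brings in everyone who completes the 24-week period, "regardless of whether they completed trial treatment or discontinued trial treatment prematurely", and adds: "During the open-label Follow-up period subjects will be treated with molgramostim".
- SAP 3.1 applies the rule to all subjects recruited under protocol version 4.0 or later.

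**Who stops double-blind drug.** Section 8.4.2 lists lack of efficacy or worsening, unacceptable AE, "Serious hypersensitivity reaction" and pregnancy. Stopping does not by itself withdraw the subject. The section's own example, a stop at Week 8, has the subject encouraged to attend through Week 24 and go on into Follow-up.

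**What points the other way.**
- Section 11.8: "Pregnant subjects will be withdrawn from further trial treatment".
- The Synopsis (overall trial design) and 9.1.1 say that Follow-up molgramostim should be stopped for disease worsening or safety concerns.
- Section 9.1.1 makes Follow-up treatment optional for subjects who entered Follow-up before national approval of Amendment 11.

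**The concern.** Read literally, the Follow-up text assigns open-label drug to a subject whose double-blind drug was stopped for pregnancy, a serious hypersensitivity reaction, an unacceptable AE or worsening. The protocol encourages exactly these subjects to stay until Week 24, so the situation follows from its own retention policy. Whether such a subject receives drug would then depend on which section the site reads. The Follow-up safety report would also mix subjects who took open-label drug with subjects who did not, under column labels that imply all were treated.

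**Working it through.** No plan figure has to be reproduced; this is a check of the text, with one short calculation for the exposure rule.

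**Step 1. Each 8.4.2 reason against the rest of the text.**

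| Reason for stopping double-blind drug | Assigned at Week 24 by 5.2, 7.1 and 9.1.1 | Text pointing the other way | Result |
|---|---|---|---|
| Pregnancy | Open-label drug | 11.8 ends further trial treatment and is not limited to the double-blind period | Direct contradiction |
| Serious hypersensitivity reaction | Open-label drug | Follow-up stop rule (safety concerns); nothing expressly bars starting | Unreconciled |
| Unacceptable AE | Open-label drug | Same stop rule; nothing expressly bars starting | Unreconciled |
| Lack of efficacy or worsening | Open-label drug | Worsening is also a Follow-up stop criterion; nothing expressly bars starting | Unreconciled |

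On the first row, the Follow-up visit lists call the open-label product trial drug, so it falls within the treatment that 11.8 ends.

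**Step 2. Does any text set a condition on starting?**
- The stop rule in the Synopsis and 9.1.1 covers stopping Follow-up drug. It sets no condition on starting it.
- The investigator discretion in 8.4.2 concerns double-blind treatment.
- The 9.1.1 exemption depends on when the subject entered Follow-up, not on why drug was stopped.
- Table 1, note d, recognises Follow-up subjects who are not treated but does not say who they are. The Amendment 11 exemption alone could account for them.

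**Step 3. The exemption itself is described in different ways.** Section 9.1.1 makes treatment optional for the whole Follow-up period. Section 7.1 makes it optional only for the last 24 weeks. SAP 3.1 goes by the protocol version under which the subject was recruited.

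**Step 4. What the SAP does with a non-starter.**
- Efficacy: SAP section 4 defines FU-MOL-INT, the subjects receiving the intermittent regimen in Follow-up. Appendix 1 produces the Follow-up efficacy tables on both FU-FAS and FU-MOL-INT, so treated subjects are already evaluated alone.
- Adverse events: Tables 14.3.1.9 to 14.3.1.13 are on FU-SAF only, and the Follow-up column labels all end in MOL FU. FU-SAF corresponds to the double-blind safety set (at least one dose of trial drug). The SAP does not say that a dose must be taken in Follow-up, so a non-starter would naturally remain in it.
- Exposure: for subjects enrolled under versions 4 and 5, SAP 5.3.9 counts from Visit 8 to Visit 11 or until treatment is discontinued. Visit 11 is 168 days after Visit 8, with a window of 14 days either way.
  - A non-starter counted to Visit 11 is credited with 168 days (168 / 7 = 24 weeks; range 168 − 14 = 154 to 168 + 14 = 182), although the true exposure is 0.
  - If the double-blind stop date is used instead, a stop at Week 8 (day 56) with Visit 8 at day 168 gives 56 − 168 = −112 days, which has no meaning.
  - The SAP has no rule for this case.

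**The case against.** The strongest reply is that a protocol is read as a whole. A specific rule such as 11.8 normally prevails over a general description of a regimen, a serum pregnancy test is scheduled at Week 24, and an investigator who stopped drug for safety would hardly restart it with a safety-concerns rule in the same section. Section 11.7 adds that no acute systemic or hypersensitivity reactions have been reported with inhaled products of this type. This tells against any claim that sites would in practice treat these subjects. It does not remove the conflict: 5.2 goes out of its way to include early stoppers, and no section makes starting depend on the reason for stopping.

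Several stronger readings are tempting, and the documents do not support them.
- **That every 8.4.2 reason is flatly contradicted elsewhere.** Only pregnancy is. For the others the defect is an unconditional assignment with no stated start condition.
- **That 8.3 is breached** because it lists "History of allergic reactions to GM-CSF". Those criteria govern entry to the trial and are not applied to Follow-up.
- **That the Visit 8 list orders dosing.** The Week 12 list also has clinic dosing and dispensing without exception, and nobody would read it as restarting drug in someone stopped at Week 8. Both are generic schedules.
- **That all these subjects would be re-dosed.** For a placebo subject, open-label drug would be a first exposure to molgramostim, although 9.1.2 gives placebo the same other constituents.
- **That the SAP treats everyone as treated.** FU-MOL-INT answers this for efficacy; the gap is in exposure and in the FU-SAF adverse event tables.
- **That a number of affected subjects can be given.** No discontinuation rate is stated. Applying an assumed rate to all 135 planned subjects would count exempt subjects and those who leave before Week 24.

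**Conclusion.** The concern holds in this form: the protocol assigns open-label molgramostim to all subjects who reach Week 24, including early stoppers, without regard to the reason for stopping. There is one direct contradiction (pregnancy, with 11.8). Three further reasons are unreconciled with 8.4.2 and the Follow-up stop rule. The Amendment 11 exemption is also described inconsistently. This is a stated rule rather than a missing detail, and a site should not have to disregard it in order to act on 11.8 or on the stop rule.

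The reach is limited. The rule binds only subjects outside the exemption, and their number cannot be derived from the documents. Follow-up data are descriptive, so the double-blind primary and key secondary analyses are unaffected. The analysis consequence is up to about 24 weeks of exposure wrongly credited to each non-starter, and Follow-up adverse event columns that mix treated and untreated subjects. That rests on reading FU-SAF as not requiring a Follow-up dose.

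**What to change.** **Protocol.** Reconcile 5.2, 7.1 and 9.1.1, and SAP 3.1 with them, with 8.4.2, 11.8 and the Follow-up stop rule. Replace the all-subjects wording with text that states, for each 8.4.2 reason, whether the subject enters Follow-up with or without open-label drug. Describe the Amendment 11 exemption in the same way throughout. Which clinical rule applies is for the sponsor to decide; none is proposed here.

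**SAP.** Keep FU-MOL-INT for efficacy. In 5.3.9, set Follow-up exposure to zero for subjects who never start open-label drug. In the FU-SAF adverse event tables, show those subjects apart from the MOL FU columns.

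**Cost.** A wording amendment, a letter to sites and a few SAP lines. No extra subjects, visits or procedures.

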9.1.2 Identity of Investigational Medicinal Products

Each vial of molgramostim contains 250 µg/mL molgramostim in 1.2 mL solution. Matching placebo will contain the same constituents but without the active molgramostim.

9.1.3 Manufacturing, Packaging and Labelling of Investigational Medicinal Product

All manufacturing and packaging will be performed in accordance with current Good Manufacturing Practice (GMP).

Individual medication kits containing double-blind trial medication for one week will be supplied in adequate amounts at the dispensing visits. Every kit will be labelled with a unique medication number, which also appear on a tear-off part of the label.

Labels will comply with local regulations and will be printed in local language.

9.1.4 Storage and Handling of Investigational Medicinal Product

The IMP must be stored at 2-8°C.

The IMP will be stored at the trial site or the at the site pharmacy as required by local regulations and laws for the participating sites. The Investigator will ensure that the IMP will be stored in appropriate conditions in a secure location with controlled access. The storage compartment must be monitored and the temperature documented. Any deviations in storage temperature must be reported to sponsor without delay. In case of a temperature deviation, the IMP must not be used until acceptance from the sponsor.

The IMP kits will be dispensed to the subject at Baseline (Visit 2), and at Weeks 4, 8, 12, 16 and 20 (Visits 3, 4, 5, 6, and 7) during the Double-blind treatment period.

Unblinded IMP kits will be dispensed to the subject at Week 24 post-randomisation and at Follow-Up Weeks 12, 24 and 36 (Visits 8, 10, 11 and 12).

Subjects will be instructed to store the kit at 2-8°C in a safe and secure place out of the reach of children. The IMP should not be frozen or shaken and not be used beyond the expiration date on the vial.

Subjects will be asked to return used and unused medication at the next clinic visit to check compliance.

9.1.5 Investigational Medicinal Product Administration and Training

The PARI eFlow nebuliser system (PARI Pharma GmbH, Germany) will be used to administer the IMP. The eFlow Nebuliser Handset is a single subject use, reusable electronic nebuliser. It includes a fine particle aerosol generator (perforated vibrating membrane) defined by a 30L mesh and an aerosol chamber that can produce aerosols with high density of active drug, precisely defined droplet size and a high proportion of respirable droplets.

All subjects, investigators and trial nurses will be trained in IMP administration and medical device maintenance procedure. The training of the subjects will be arranged prior to administration of the subject's first dose of IMP and checked in clinic on first dosing. The subject will also receive written instructions.

The subject will administer the first dose of IMP post randomisation at the Baseline visit (Visit 2) under the supervision of trial personnel.

9.2 Method of Assigning Subjects to Treatment Groups

At Screening (Visit 1), the subject will be assigned a site-specific subject number that will continue to be the unique identifier throughout the trial. The subject number will be generated automatically by the electronic data capture system used in the trial. The subject number will be in the following format XX-YYY. The letter XX is the site number and YYY the consecutive subject number starting at 001 at each site.

At the Baseline visit, eligible subjects will be centrally assigned to one of the three Double-blind treatment groups through an interactive web response system (IWRS). Randomisation will be stratified according to whether or not a WLL has been conducted within 2 months prior to the Baseline visit. The system will assign unique medication kits number to each subject at each dispensing visit.

Medication kits to be used in the Follow-up period are not blinded.

9.2.1 Randomisation

A randomisation list will be prepared by TFS's statistical department, who will store the list in a secure folder until unblinding has taken place.

9.2.2 Subject Identification List

The investigator will maintain a list of all subjects enrolled in the trial at the site. This list includes each subject's identity, date of enrolment and corresponding subject number so that any subject may be identified if required for any reason.

9.3 Blinding

All subjects will inhale IMP once daily during the Double-blind treatment period. Blinding will be ensured by the use of a matching placebo.

The packaging and labelling of the investigational products for the Double-blind treatment period will contain no evidence of their identity and it is not considered possible to differentiate between the investigational products solely by sensory evaluation.

9.3.1 Breaking the Randomisation Code

Unblinding of a single subject may occur for emergency purposes only. Investigators should note that the occurrence of a Serious Adverse Event (SAE) should not routinely precipitate the immediate unblinding of the label. If the treating physician considers it necessary to unblind the study medication for medical reasons, unblinding can be done using IWRS – and if possible, after prior contact with the Sponsor. The date and the event making it necessary to unblind the treatment randomization have to be documented in the patient files and in the case report form (CRF). The Sponsor will immediately be notified in case of emergency unblinding by an investigational site. In the case of a potential suspected unexpected serious adverse reaction (SUSAR) for an individual subject, Premier Research may break the blind. All investigational sites and the Sponsor's Pharmacovigilance Representative (Premier Research) have access to unblinding in the IWRS.

A Data Safety Monitoring Board (DSMB) will review unblinded safety data as part of the safety surveillance of the trial. A statistician from TFS who is independent from the trial will make the unblinded safety and tolerability data listings available to the DSMB according to TFS SOPs and the Statistical Analysis Plan. All study team members will remain blinded.

Unblinding of the clinical trial will take place when a final validated database for the 24-week double-blind period has been produced, the statistical analysis specified in this protocol has been reviewed in relation to the blinded data actually obtained and the Statistical Analysis Plan (SAP) has been approved.

9.4 Prior and Concomitant Therapy

The use of concomitant medicines or other treatment regimen during the 24-week Double-blind treatment period should be kept at a minimum and should be kept as stable as possible. Medication/treatment, which is considered necessary for subject safety and well-being, may be given at the discretion of the investigator. Examples of such medications/treatments are:

- WLL (rescue therapy) - The criteria for performing WLL is clinical worsening of aPAP based on symptoms, reduced exercise capacity and/or findings of hypoxemia or desaturation according to the Investigator's judgement. The reason(s) for conducting WLL will be documented.
- Oxygen supplementation

Sputum modifying medications such as carbocystein and ambroxol are prohibited for participating subjects in the Double-blind period of this trial. Medications detailed in the exclusion criteria which are rituximab and therapy associated with significant immunosuppression are also not allowed (e.g. more than 10mg/day systemic prednisolone) while the subject is treated with IMP in the Double-blind or Follow-up periods. Other rhGM-CSF products are not allowed during the Double-blind or Follow-up periods.

For subjects who discontinue the double-blind trial treatment and for all subjects in the Follow-up period, use of medications to specifically treat aPAP will be recorded in the eCRF. Information will be collected regarding:

- concomitant medications, treatments and procedures used to treat aPAP
- medication or treatments which may alter the course of aPAP
- medication or treatments used to treat AEs

No other information on concomitant medications, treatments or procedures in the Follow-up period will be collected.

The use of concomitant medication by the subject must be recorded in the appropriate sections of the eCRF (*Section 10.3.3*).

